5.4.2 ISA101b Dose Modifications, Timing and Precautions

ISA101b dose modifications are not allowed.

In order to assure the maximal immune response to ISA101b, the second 2 doses of ISA10b should each be given at the expected myeloid nadir, i.e. 14 days after administration of cisplatin. This timing should be maintained if the dose of cisplatin is delayed for any reason.

Patients receiving ISA101 in Montanide should be observed for at least 4 hours after vaccination to provide means for immediate treatment of allergic reactions should that be necessary (precautions include availability of staff well-trained in resuscitation, intravenous access for administration of fluids, antihistamines and corticosteroids, and epinephrine for intramuscular injection).

The dose of ISA101b will not be adjusted.

However, ISA101b will be discontinued in case of severe systemic allergic reaction, characterized by dyspnea, urticarial, severe generalized skin rash or other signs of severe systemic allergic reaction.

Local injection site reactions are expected with the administration of ISA101b. Severe ISRs requiring discontinuation of ISA101b have been reported. The investigator should use clinical judgement in administering further ISA101b if the reactions are particularly severe and/or increasing with successive doses of ISA101b. If ISA101b has to be discontinued for toxicity related to ISA101b, patient may continue treatment on trial with Cisplatin, IMRT, and pembrolizumab with PI approval. If a patient does not meet criteria to discontinue ISA101b, however declines further vaccine for any reason the patient can only stay on the trial if at least 2 of the vaccine doses have been given.

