5.5.12 Radiation Therapy Treatment Interruptions

Treatment interruptions are strongly discouraged. Treatment breaks must be clearly indicated in the treatment record when they occur. Patients who have treatment interruptions for >3 weeks will be taken off study. The interruption of radiation therapy for grade 4 mucositis / dermatitis / dysphagia is at the discretion of the treating radiation oncologist. Treatment breaks, if necessary, ideally should not exceed five treatment days at a time and ten treatment days total. Treatment breaks should be allowed only for resolution of severe acute toxicity and/or for intercurrent illness and not for social or logistical reasons. Cisplatin, pembrolizumab and ISA101b will not be administered during radiotherapy treatment breaks.

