5.6 Duration of Treatment and Follow-up

Complete treatment includes the course of definitive radiotherapy with concurrent chemotherapy and a total of 17 doses of pembrolizumab. In the absence of treatment delays due to adverse event(s), treatment may continue until disease progression or until one of the following criteria applies:

- Intercurrent illness that prevents further administration of treatment,
- Unacceptable adverse event(s),

- Patient decides to withdraw from the study, or
- General or specific changes in the patient's condition render the patient unacceptable for further treatment in the judgment of the investigator.

Patients will be administered pembrolizumab 200 mgs q 3 weeks starting week -1 for a total of 17 doses.

Patients will be followed for progression and survival using Standard of care intervals. Patients removed from study for unacceptable adverse event(s) will be followed until resolution or stabilization of the adverse event.

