5.7 Participant Discontinuation Criteria

Discontinuation of study intervention does not represent withdrawal from the study.

As certain data on clinical events beyond study intervention discontinuation may be important to the study, they must be collected through the participant's last scheduled follow-up, even if the participant has discontinued study intervention. Therefore, all participants who discontinue study intervention prior to completion of the protocol-specified treatment period will still continue to be monitored in this study and participate in the study visits and procedures as specified in Section 2.2 unless the participant has withdrawn from the study.

Participants may discontinue study intervention at any time for any reason or be discontinued from the study intervention at the discretion of the investigator should any untoward effect occur. In addition, a participant may be discontinued from study intervention by the investigator or the Sponsor if study intervention is inappropriate, the study plan is violated, or for administrative and/or other safety reasons.

A participant must be discontinued from study treatment but continue to be monitored in the study for any of the following reasons:

- The participant or participant's legally acceptable representative requests to discontinue study intervention
- After prolonged study intervention interruption that prohibits restarting study intervention if agreed upon with the Sponsor
- Radiographic disease progression [outlined in Section 6.1.4](#).
- [Any progression or recurrence of malignancy, or any occurrence of another malignancy that requires active treatment](#)
- Any study intervention-related toxicity specified as a reason for permanent discontinuation as defined in the guidelines for dose modification due to AEs in Section 5.2.4.
- The participant has a medical condition or personal circumstance which, in the opinion of the investigator and/or sponsor, placed the participant at unnecessary risk from continued administration of study treatment.
- The participant has a confirmed positive serum pregnancy test

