5.8.1 DLT

DLT is defined as the occurrence of a severe adverse event (AE) listed below that is *at least possibly* related to ISA101b and pembrolizumab and occurs within 24 weeks of the initiation of ISA101b or pembrolizumab and leads to at least a two week delay in CRT. AEs will be graded according to NCI CTCAE version 5.0. The Data Safety and Monitoring Committee of the H&N Program at UPMC Hillman Cancer Center (HCC) will determine causality and whether to remove the suspension and permit the trial to proceed, in consultation with the Principal Investigator, key co-Investigator(s), ISA and Merck.

DLT Definition:

Since autoimmune/inflammatory events may occur at any time during the course of treatment, and may occur with evidence of clinical benefit, the following criteria will be used to define DLT:

- Any \geq Grade 3 non-hematologic toxicity **except**:
 - Grade 3 in-field radiation dermatitis for which IMRT is held \leq 1 week (5 fractions)
 - Grade 3 mucositis for which IMRT is held \leq 1 week (5 fractions)
 - Asymptomatic Grade 3 hypomagnesemia or hypokalemia, which corrects to Grade \leq 2 with replacement therapy
 - Grade 3 dysphagia
 - Grade 3 pain
 - Grade 3 weight loss
 - Grade 3 fatigue
- An alanine or aspartate amino transaminase elevation of greater than three times the upper limit of normal with concurrent elevation of bilirubin two times the upper limit of normal attributable to pembrolizumab should be considered a DLT. Patients meeting this criterion should be permanently discontinued from pembrolizumab.
- Autoimmune toxicity of any grade requiring systemic corticosteroids or other anti-inflammatory that cannot be tapered off in less than 12 weeks.
- Delay in completion of radiation therapy >10 fractions, or inability to complete prescribed IMRT course, due to immune toxicity at least possibly attributed to pembrolizumab or ISA101b.
- Grade \geq 3 neutropenia with fever (oral temperature $> 39^{\circ}\text{C}$)
- Grade \geq 3 thrombocytopenia with bleeding
- Grade \geq 3 local injection site reaction at the site of ISA101b injection
- Grade \geq 3 systemic allergic following ISA101b injection

Patients who experience a DLT to pembrolizumab will receive no additional doses of pembrolizumab and will be withdrawn from the protocol. Patients who experience a DLT to ISA101b will receive no additional doses of ISA101b but may continue on protocol treatment (cisplatin, IMRT, Pembrolizumab) with PI approval.

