10.2 Sample Size

Sample size is determined by the primary objective of testing whether the addition of ISA101b+ pembrolizumab improves two year progression-free survival in HPV-16+ OPSCC patients treated with cisplatin CRT. The historical control for the study is based part upon the results of O’Sullivan and Huang⁴⁵ in which the probability of 3 year OS was approximately 65% for high risk (Class III, T4 or N3, age < 70) HPV+ patients treated with chemoradiation and that 3 year OS is an approximation of two year PFS. For the combination of pembrolizumab, ISA101b, and chemoradiation to be considered for further study it is desirable to demonstrate a 25% relative improvement in 2 year PFS from 65% to 81%. We plan to devote 2 years to patient accrual with 1 additional year of follow-up after closing accrual. Using a one-tailed exponential test (using the maximum likelihood estimator for the hazard rate of the exponential distribution) at $\alpha = .10$, 45 patients will provide 87% power to reject the null hypothesis of 65% two year PFS when the underlying two year PFS is 81%. In order to obtain 45 evaluable patients, we will oversample through a total accrual of 50 fully treated patients. Thus, the planned enrollment to this trial is 50 patients.

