10.4 Proposed Data Analysis

At study completion a one-sided one sample exponential test will be conducted to detect an increase above the presumed historical control rate of 65% PFS at two years. If this test is rejected at $\alpha = .10$, the treatment regimen will be considered sufficient for further investigation. Probabilities of times to local recurrence, regional recurrence and death will be estimated by the Kaplan-Meier method with 95% confidence intervals as well as by cumulative incidence if needed to adjust for the competing risk of death. Treatment-related toxicities will be summarized by frequency and grade. If intervening deaths are observed cumulative incidence plots and analysis of competing risks may be conducted.

A series of correlative studies will be conducted based on blood and tissue samples collected prior to treatment among patients treated with pembrolizumab + ISA101b. The first item below is a planned analysis with alpha spending of 10% to be distributed among the biomarker endpoints.

1. Test the association of baseline H score of PD-L1 tumor expression, circulating antibodies against HPV, EGFR and p53 and other tumor antigens upon PFS using proportional hazards regression adjusting if needed for confounding variable such as T stage, N stage and smoking history.
2. Estimate and test the effect of ISA101b using paired (pre/post pembrolizumab +/- ISA101b) values of immune and inflammatory makers will be compared with the Wilcoxon test.
3. Compare differences in circulating HPV, EGFR, p53 and other tumor antigen antibodies using baseline versus 3-6 weeks or 6 months post-treatment. Linear mixed effect models will be used to evaluate the longitudinal response.
4. Estimate and characterize sequential series of blood samples pre- and post-treatment for a series of immune and inflammatory markers. These will be specified by the investigator and due to exploratory nature of these additional tests, p values will be adjusted for false discovery.

The change in CD4, CD8, FOXP3, PD-1, PD L1, and PD-L2 over time will be described graphically. An exploratory analysis of the relationship between those changes and PFS will be conducted by proportional hazards regression.

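### No primary efficacy set is defined, so which 45 of the 50 patients enter the PFS test could depend on what happens after treatment starts

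*Combined protocol and SAP*

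**What the plan says.** Section 10.2 gives 87% power with 45 patients for 65% versus 81% two-year PFS at one-sided alpha 0.10, and continues: "In order to obtain 45 evaluable patients, we will oversample through a total accrual of 50 fully treated patients". Its closing sentence gives planned enrolment as 50. Section 10.4 states the test and the go rule: "At study completion a one-sided one sample exponential test will be conducted to detect an increase above the presumed historical control rate of 65% PFS". It does not say which patients enter the test, and it has no all-treated rule and no rule on replacement. Its sequencing paragraph describes the 45 as everyone who receives pembrolizumab.

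Four rules remove patients for reasons that arise after treatment starts:

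- **Section 5.1.5:** patients who need a prohibited treatment are to be removed from the trial.
- **Section 5.4.2:** for a patient who declines further vaccine without meeting the stopping criteria, "the patient can only stay on the trial if at least 2 of the vaccine doses have been given".
- **Section 5.5.12:** "Patients who have treatment interruptions for >3 weeks will be taken off study".
- **Section 5.8.1:** "Patients who experience a DLT to pembrolizumab will receive no additional doses of pembrolizumab and will be withdrawn from the protocol".

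Section 5.7 says the opposite about follow-up: "Discontinuation of study intervention does not represent withdrawal from the study". It requires patients who stop treatment, including for progression, to stay under observation. Section 6.1.3.7 counts PFS from treatment initiation, with progression or death from any cause as the event.

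**The concern.** The plan expects about five of 50 patients not to count and never says who they are. The removal rules give reasons for not counting someone: toxicity, interrupted radiotherapy, a declined vaccine, a prohibited medication. Each may be associated with a worse prognosis. If such patients leave the study, or are judged not evaluable, the primary set is chosen partly on post-treatment events, yet PFS is still counted from the first dose.

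This is a single-arm comparison with a fixed rate of 65%, so no control arm undergoes the same selection. The trial is open-label (section 11.3), so the set could be settled with outcomes known. One go decision rests on this test, and its 10% error rate holds only if the set does not depend on outcome.

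**Working it through.** **Inputs.** Section 10.2: two-year PFS 65% (null) and 81% (alternative), one-sided alpha 0.10, accrual A = 2 years, further follow-up F = 1 year, n = 45 or 50. Table 2: first vaccine at week -2, IMRT in weeks 0 to 6, so IMRT ends 2 + 7 = 9 weeks after the first dose. Assumptions: constant hazard and uniform accrual.

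**Step 1: reproduce the plan's power.** Hazards are h0 = -ln(0.65)/2 = 0.2154 and h1 = -ln(0.81)/2 = 0.1054 per year. The probability of an observed event is 1 - (e^(-hF) - e^(-h(A+F)))/(hA). For n = 45 this gives 15.52 expected events under the null and 8.48 under the alternative.

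On the log-hazard scale, power = Φ{[ln(h0/h1) - 1.2816/√15.52] × √8.48} = Φ{(0.7151 - 0.3253) × 2.912} = Φ(1.135) = 87.2%. The hazard scale gives 86.5%. The stated 87% is reproduced. The step from 45 to 50 is a 10% loss allowance: 45/0.90 = 50.

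**Step 2: power with all 50.** Expected events are 17.25 and 9.43. Power = Φ{(0.7151 - 0.3086) × 3.070} = Φ(1.248) = 89.4%. The hazard scale gives 89.8% and simulation 88-90%.

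**Step 3: false-go rate by who is left out.** True two-year PFS is 65%. Each scenario was simulated with 100,000 trials; the range is over four versions of the exponential test.

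| Patients analysed | False-go rate |
|---|---|
| All 50 | 8.4-9.8% |
| 45, with 5 exclusions unrelated to outcome | 8.2-9.5% |
| 49, earliest failure excluded | 13-15% |
| 48, two earliest failures excluded | 19-21% |
| 47, three earliest failures excluded | 27-29% |
| 46, four earliest failures excluded | 36-37% |
| 45, five earliest failures excluded | 44-46% |
| Event-free to week 9, end of IMRT | 17-19% |

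In the last row the expected number of failures removed is 50 × (1 - e^(-0.2154 × 9/52)) = 1.8.

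**Step 4: a check without the exponential test.** With 50 patients at 65%, 32.5 are expected to be progression-free at two years. Dropping five failures turns 32.5/50 = 65% into 32.5/45 = 72.2%. An exact binomial rule of at least 34 of 45 has a nominal error of 9.0%. If the 45 are 50 patients less five failures, the error is 38.9%.

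**The case against.** The strongest reply is that the quoted sentence is only an attrition allowance. No section excludes early progressions or deaths from the primary test. Section 5.7 keeps patients who stop treatment under observation, section 5.6 provides for progression and survival follow-up, and section 6.1.3.7 makes early progression an observed event, so an early progressor is plainly evaluable. The removal rules are triggered by toxicity, interruption, prohibited treatment or refusal, not by progression, and the vaccine and radiotherapy rules act well before the first response scan at weeks 20-22. If the 45 are simply those who receive pembrolizumab, as in the sequencing paragraph of section 10.4, losses fall in the single week between first vaccine and first pembrolizumab. At the null hazard that week holds about 50 × (1 - e^(-0.2154/52)) = 0.2 failures.

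Much of this stands. It rules out saying that the plan removes early failures, and it makes the earliest-failure rows worst cases. It does not supply an analysis set. Follow-up provisions do not say who enters the test, and the wording of sections 5.1.5, 5.4.2 and 5.5.12 conflicts with section 5.7. In section 5.8.1, withdrawal from the protocol could mean treatment only, but the text does not say so.

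Two stronger readings are tempting and are not supported:

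- A reader might join *fully treated* to section 5.6: "Complete treatment includes the course of definitive radiotherapy with concurrent chemotherapy and a total of 17 doses of pembrolizumab". That would require being event-free for about 49-50 weeks. Conditional two-year PFS would be about 0.65/0.817 = 79.6% and the false-go rate about 86-89%. But section 10.2 equates the 50 with planned enrolment, which cannot hold if all 50 must finish 17 doses, and section 5.6 does not use the terms of section 10.2.
- A reader might infer that the 65% benchmark comes from a cohort analysed without exclusions. The documents do not say how that cohort was assembled.

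**Conclusion.** The point holds as an undefined primary set that can depend on post-treatment events, not as a planned exclusion of early failures. The false-go rate stays at about 9% if the five losses are unrelated to outcome and reaches about 45% if they are the five earliest failures. One excluded early failure is enough to pass the nominal 10%. Requiring patients to be event-free to the end of IMRT gives about 18%. Where the trial would fall in this range cannot be known from the documents. The figures rest on a constant hazard, uniform accrual and a true rate of 65%. This should be settled before analysis: the go decision depends on it, and an all-treated set removes the problem at no cost in power.

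**What to change.** - In sections 10.2 and 10.4, define the primary efficacy set as all patients who start protocol treatment (first ISA101b dose; 50 planned), without replacement, with PFS from treatment initiation.
- Restate power as about 89% at n = 50; 45 gives 87%.
- Define *evaluable* and use it for a sensitivity analysis only.
- Reconcile the three descriptions: 50 fully treated, 50 enrolled, and 45 who receive pembrolizumab.
- Reconcile the off-trial, off-study and off-protocol wording in sections 5.1.5, 5.4.2, 5.5.12 and 5.8.1 with section 5.7, so that patients who leave treatment stay in PFS and survival follow-up. The treatment rules themselves are unchanged.

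The cost is wording only. The observed PFS may be slightly less favourable than in a selected set.

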10.3 Continuous Monitoring for Treatment Delay

A Phase I trial of pembrolizumab plus cisplatin chemoradiation in HNSCC has been reported, demonstrating safety of this combination. Thus, unexpected toxicities are not anticipated. While the ISA101b vaccine may lead to allergic type reactions, it can be readily discontinued in this case, with little harm to the patient as long as overall standard of care therapy continues. Thus, the primary monitoring is for delay in delivery of potentially curative chemoradiation therapy.

A Bayesian continuous monitoring schema will be implemented to protect against unexpected delays of two weeks or greater in the post-vaccine administration of radiation + DDP due to adverse effects of ISA and/or pembrolizumab. A 30% rate of treatment delay is considered unacceptable. We will suspend the trial pending DSMB review if the posterior probability that the 2 week treatment delay rate exceeds 30% is greater than 50%. In addition, the study will be suspended for any death that is possible related to the administration of investigational products. In such a case, a thorough assessment of the safety profile must be conducted, and the risk benefit consideration must be justified for any additional subject enrollment. Monitoring will commence with the third patient completing ISA101b + pembrolizumab and continue, if needed, through 50 patients. If π denotes a random variable representing the proportion of subjects who experience a delay of two weeks or more, we assume π has a prior beta distribution with a mean of .15 and parameters $a = 1.5$ and $b = 8.5$.

Selected values of the posterior probability PP ($\pi \geq .30$ | # delays and prior) are shown in the table below. Also shown are selected binomial probabilities of suspending the study for observed count of observation failures.

Number Patients	Number Delays	Min PP($\pi \geq .30$)	P(x > # delays $\pi = .30$)
3 - 4	3	.541	.084
5 - 7	4	.558	.126
8 - 11	5	.513	.210
12 -14	6	.530	.219
15 - 17	7	.545	.225
18 - 21	8	.511	.277
22 - 24	9	.525	.275
25 - 27	10	.539	.272
28 - 31	11	.509	.312
32 - 34	12	.522	.307
35 - 37	13	.534	.302
38 - 41	14	.508	.335
42 - 44	15	.520	.328
45 - 47	16	.531	.322
48 - 50	17	.541	.316

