5. TREATMENT PLAN

The first ISA101b vaccine will be initiated 2 weeks prior to cisplatin-IMRT, and one week prior to the first dose of pembrolizumab. Vaccines will continue for 2 additional administrations at weeks 2 and 5, +/- 1 days from the successive pembrolizumab infusions. Pembrolizumab will be initiated 1 week prior to cisplatin-IMRT at the dose of 200 mg IV q3 weeks (+/- 3 days). Pembrolizumab will be continued concurrently through cisplatin-IMRT (weeks 2, 5, and continued for a 42 week maintenance period after completion of cisplatin-IMRT for a total pembrolizumab treatment period of 50 weeks (17 doses). NOTE: Per discretion of the treating investigator, the week 8 dose of pembrolizumab may be delayed up to 3 weeks for recovery of acute toxicities from chemoradiotherapy. This dose would be considered delayed, and all subsequent doses would be administered at a q3 week interval (+/- 3 days) until completion.

Table 2. Treatment Plan

- **IMRT 70 Gy (35 fractions, 2Gy/fraction)**
- **Cisplatin 100 mg/m² q21 days X 2 doses**
- **Pembrolizumab 200 mg q3week IV (flat dose) X 17 doses**
- **ISA10b Vaccine (Three vaccinations given 2 weeks prior to CRT and one week prior to pembrolizumab, then in weeks 2 and 5 during CRT on the same days (+/- 1 day) as pembrolizumab)**
- **PD-L1 status will not be used during this trial for treatment decisions**

Patients will be administered pembrolizumab 200 mg q3 weeks starting week -1 for a total of 17 doses.

Table 2.	Week of Treatment									
	-2	-1	0	1	2	3	4	5	6	8-47
IMRT			X	X	X	X	X	X	X	
Cisplatin			X			X				
Pembrolizumab **		X			X			X		X
ISA101b	X				X*			X*		

*ISA101b may be administered +/- 1 day of pembrolizumab administration for Weeks 2 and 5.

**Pembrolizumab 200mg IV q 3 weeks is given starting week -1 and continued for a total of 17 doses.

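### Section 10.3 ties the first look at CRT delay to completing pembrolizumab, read literally about 40 weeks after a delay is known, and tabulates single-look rather than cumulative suspension probabilities

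*Combined protocol and SAP*

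**What the plan says.** Section 10.3 names delay of chemoradiation as the primary monitoring target. The scheme is meant to "protect against unexpected delays of two weeks or greater in the post-vaccine administration of radiation + DDP" caused by ISA101b and/or pembrolizumab. The rule reads: "We will suspend the trial pending DSMB review if the posterior probability that the 2 week treatment delay rate exceeds 30% is greater than 50" per cent. The prior is Beta(1.5, 8.5), with mean .15. The start is set by one sentence: "Monitoring will commence with the third patient completing ISA101b + pembrolizumab and continue, if needed, through 50 patients".

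The section gives no week or dose number for completing. Elsewhere:

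- Section 5 gives ISA101b at weeks -2, 2 and 5, and pembrolizumab every 3 weeks from week -1 "for a total pembrolizumab treatment period of 50 weeks (17 doses"). Section 5.6 includes the 17 pembrolizumab doses in its description of complete treatment.
- Section 5.5.1 gives IMRT over 7 weeks, so CRT is scheduled to end after week 6.
- Section 5.8 says DLT is monitored continuously for the concurrent combination, makes excess DLT that delays CRT by more than 2 weeks a trigger for suspension, and refers to 10.3 for the details.
- Section 5.8.1 makes a CRT delay of at least two weeks part of the DLT definition and adds: "Patients who experience a DLT to pembrolizumab will receive no additional doses of pembrolizumab and will be withdrawn from the protocol". Section 5.5.12 takes patients off study after a radiotherapy interruption of more than 3 weeks.

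The table in 10.3 gives 15 boundary rows. Its last column is headed P(x > # delays) at π = .30, and the text introduces it as follows: "Also shown are selected binomial probabilities of suspending the study for observed count of observation failures".

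**The concern.** The event being monitored is known by about the end of CRT, yet the literal start of monitoring depends on a course of treatment that runs some 40 weeks longer. A rule meant to protect potentially curative CRT would then first be applied when many patients had already passed the period it protects.

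The start sentence also leaves the denominator open. The table heads its first column Number Patients without saying who is counted, and completers are the only group the start sentence names. Patients whose CRT is delayed by pembrolizumab toxicity are among those least likely to complete it.

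Finally, a committee that takes the last column as the chance of suspending would misjudge how often the rule fires, because the rule is applied repeatedly and the column describes one look.

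**Working it through.** **1. Reproduce the table.** With x delays in n patients the posterior is Beta(1.5 + x, 8.5 + n - x). Its upper tail at .30, with n at the top of each row's range, matches all 15 tabulated posterior values. Examples: 3 of 4 gives .541; 17 of 50 gives .541. The rule cannot fire before patient 3: 2 of 2 gives .440 and 3 of 3 gives .614.

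**2. Last column.** Every entry equals the binomial P(X >= # delays) at π = .30, again with n at the top of the range:

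| n | # delays | Tabulated | P(X >= # delays) | P(X > # delays) |
|---|---|---|---|---|
| 4 | 3 | .084 | .084 | .008 |
| 50 | 17 | .316 | .316 | .218 |

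**3. Cumulative suspension probability.** Let d(n) be the boundary at n patients and q(n, k) the probability of k delays among n patients with no suspension so far. Then q(n, k) = q(n-1, k)(1 - p) + q(n-1, k-1)p. From n = 3 on, the mass at k >= d(n) is removed and added to the suspension probability.

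| True delay rate p | Suspended by patient 22 | Suspended by patient 50 |
|---|---|---|
| 15% | .04 | .038 |
| 30% | .39 | .557 |
| 40% | .73 | .925 |
| 50% | .93 | .997 |

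(At 15% almost all suspensions occur early, so the two entries agree after rounding.)

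**4. Timing, literal reading.**

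- Dose 17 falls at week -1 + 16 × 3 = 47, which is 49 weeks after the first ISA101b dose at week -2.
- CRT occupies weeks 0 to 6, so it ends at the start of week 7, 9 weeks after the first dose. The gap is 47 - 7 = 40 weeks.
- Uniform accrual (assumed; section 10.2 gives only 50 patients in 2 years) is 50/104 = 0.481 per week. If patient 1 starts at time 0, patient 3 starts at 2/0.481 = 4.2 weeks.
- The first look is at 4.2 + 49 = 53.2 weeks.
- Enrolled by then: 53.2 × 0.481 = 25.6, so patients 1 to 26.
- Past CRT by then: (53.2 - 9) × 0.481 = 21.2, so patients 1 to 22.
- The count is 21 if CRT takes 2 weeks longer. It is 22 or 23 if completion means the stated 50-week period, or dose 17 after the permitted 3-week delay of the week 8 dose.

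**5. Timing, concurrent-phase reading.** If completing means the last joint dose at week 5, the first look is at 4.2 + 7 = 11.2 weeks. Enrolled: 11.2 × 0.481 = 5.4, so 6 patients. Past CRT: (11.2 - 9) × 0.481 = 1.1, so 2 patients.

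**6. Denominator.** Under section 5.8.1 a patient with a pembrolizumab DLT stops the drug and is withdrawn from the protocol, and a DLT by its opening definition involves a CRT delay of at least two weeks. Under section 5.5.12 an interruption of more than 3 weeks also ends participation. If Number Patients means completers, both groups can drop out of numerator and denominator.

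**The case against.** The strongest defence is that week 47 is only one reading. The scheme is called continuous, its boundaries begin at 3 patients, section 5.8 ties it to the concurrent combination, the DLT window in 5.8.1 is 24 weeks, and the two agents overlap only through CRT. That reading is reasonable and gives about 2 patients past CRT instead of about 22. It does not settle the text: section 5.8 sets no threshold of its own and refers back to 10.3, whose one start sentence names completion.

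A reader might go further and infer that some 22 patients would be unmonitored. The documents do not support that. Toxicity is assessed weekly during CRT, DLTs are monitored continuously, a possibly related death suspends the study, and the disease-center DSMB and the DSMC meet monthly with power to suspend accrual. What may come late is the only rule with a numerical delay threshold.

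A reader might also infer that delayed patients who stop pembrolizumab are never counted. The start sentence fixes when monitoring begins, not who is counted, and the rate is defined over subjects: "If π denotes a random variable representing the proportion of subjects who experience a delay of two weeks or more". Section 5.7 keeps patients who stop treatment under observation, and a patient with an ISA101b DLT may continue with approval. Omission is a risk of unclear wording, not a stated rule.

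Nor is the rule blind once it starts. If all 22 patients past CRT are counted at the first look, that look alone suspends with probability .86 at a 50% delay rate, and looks from 22 to 50 reach .996. The loss is in time.

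On the table, the strict inequality may be an artefact of text extraction, and the column does not set the boundaries. The gap between single-look and cumulative probabilities remains whichever sign was printed.

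**Conclusion.** The point holds as a defect of definition in the plan's only quantified CRT-delay rule. Neither the trigger nor the denominator is fixed, and the two available readings put about 22 (21 to 23) or about 2 patients past CRT at the first look. Both counts assume uniform accrual; slower early accrual would lower the larger one. Under the literal reading, with all patients past CRT counted, the looks from patient 3 up to about patient 21 are not available in real time. That is where much of the rule's protection lies when the true delay rate is 30% to 50%. If only completers are counted, the early rows can be used, but late and on a group from which delayed patients may be missing. These are alternatives and should not be added together.

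The table point stands regardless of how completing is read. The boundaries and posterior probabilities are correct, but the last column is not the probability that a continuously applied rule suspends the trial. At a 30% delay rate that probability is .557 by patient 50, against .316 in the table. The cumulative figures assume independent delays and a look after every patient from the third.

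**What to change.** In section 10.3:

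- Start monitoring with the third patient to reach the scheduled end of CRT or a 2-week delay attributed to ISA101b and/or pembrolizumab, whichever comes first.
- Use as denominator every patient who received at least one dose of ISA101b or pembrolizumab and reached that point, whether or not treatment continues.
- Count a delay on the day it reaches 2 weeks.
- Relabel the last column P(X >= # delays), single look, and add the cumulative suspension probabilities by 50 patients: .038 at 15%, .557 at 30% and .925 at 40%.

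Reconcile this text with sections 5.5.12, 5.8 and 5.8.1, so that a patient withdrawn or taken off study still counts towards the delay rate, and so that the delay is worded alike throughout (5.8 says more than 2 weeks; 5.8.1 and 10.3 say at least two).

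The cost is a few sentences, one relabelled column and three added figures. The prior, the 30% and 50% thresholds and the boundaries stay as they are.
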